4 STUDY DESIGN AND ENDPOINTS

4.1 Description of the Study Design

This study is designed as an open label study of a therapeutic intervention in subjects who have sustained mTBI. At least 400 subjects aged 14 to 45 inclusive will be enrolled in this study at up to 5 study sites. Subjects will be randomly assigned with a ratio of 1:1 to complete either graded exercise or passive stretching. The study sites will have well-established concussion research programs and referral populations.

The therapeutic intervention is either 20 minutes daily of graded exercise or 20 minutes daily of passive stretching delivered through the ClearPlay© mobile application, downloaded to an Apple i-touch or i-phone device, used in conjunction with a wrist-worn heart rate monitoring device (Waveband®). The sponsor will provide one i-touch or i-phone to each subject to provide them with access to ClearPlay App. This device will also allow subjects to access music for use during exercise or stretching.

Randomization of each subject will occur when the subject has completed all of their Baseline physiologic testing (Ice Bucket Test, ClearHeart© and BCBT) on Day 0.

[figure not shown]
Both the site staff treating subjects and the subjects themselves will be aware of the assigned exercise regimen. Subjects will be stratified based on baseline scores on the PCSS (threshold ≥ 30).

The study consists of 2 study visits and 3 remote telephone visits between the 2 study visits:

- Study Visit 1 (Day 0) – Screening/Baseline visit: within 3 to 14 days of concussion. This visit will serve as a screening visit, to determine eligibility to participate in the study. Eligible subjects will be enrolled, and baseline assessments performed;
- Remote telephone safety assessments – Day 14, Day 28 and Day 42 for safety follow up;
- Study Visit 2 – Follow-up visit: 8 weeks following enrolment (Day 56).

A schematic diagram of the study design is presented in Figure 2.

Figure 2: Study Design

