To validate the performance of ClearHeart© against ice bucket testing.	
 • Bland-Altman plots will be used to evaluate the agreement between HR measured by ClearHeart© and ice bucket testing. • Bland-Altman plots will be used to evaluate the agreement between BP measured by ClearHeart© and ice bucket testing.
To validate the performance of ClearNeck© against examination of the neck	
 • Correlations will be used to assess the association between results obtained through ClearNeck© testing and those obtained during the neurologic examination for neck range of motion and tenderness.

Abbreviations: ASI = Anxiety Sensitivity Index, BAI = Beck Anxiety Inventory, BCBT = Buffalo Concussion Bicycle Test, BESS = Balance Error Scoring System,; BP=blood pressure, BSI = Brief Symptom Inventory, CAARS = Conners' Adult Attention Deficit Hyperactivity Disorder Rating Scale, CES-D = Center for Epidemiologic Studies - Depression Scale,; HRV = heart rate variability; mTBI = mild traumatic brain injury; PCSS = Post-Concussive Symptom Scale, SNP = single nucleotide polymorphisms

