6.3.2 Randomization

A computer-generated randomization schedule will be prepared by a statistician prior to the start of the study. Treatment allocation will be made per the randomization list.

After signing the informed consent form/providing assent, subjects will be administered the screening instruments via REDCap Cloud, along with generation of unique subject ID.

Once eligibility has been established, subjects must proceed to complete all Baseline assessments. The Order of Assessment is listed in Section 8.1, Table 4. Randomization of each subject will occur when the subject has completed all of their Baseline physiologic testing on Day 0.

The subject will be assigned a unique randomization number, which will be allocated sequentially based on the pre-determined randomization schedule, and according to their chronological order of inclusion in the study.

Both the unique subject ID and randomization numbers will be used to identify the subject throughout the study period and on all study-related documentation.

Stratification: randomization will be stratified at each enrolment site by the baseline symptom severity score on the PCSS (threshold $<$ or ≥ 30). The baseline PCSS score is reflective of multiple pre-morbid, neurologic, psychologic, and other factors that collectively are likely to significantly impact the presence of PCSS. Rather than stratify the population based on

individual factors, the single composite measure should provide the most efficient and effective starting point for this clinical trial.

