7.6 Evaluation of Neck Range and Motion

The evaluation of neck range and motion will be performed using 2 different tests. The neurologic examination will be completed first followed by the ClearNeck© assessment.

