8 STUDY SCHEDULE OF EVENTS

8.1 Order of Assessments

The order of assessment for each subject is dependent on their assigned subject identification numbers. Refer Table 4 for detail.

Table 4: Order of Assessments :

Subjects Assigned to ODD numbered subject identification numbers	Subjects Assigned to EVEN numbered subject identification numbers
Biomarker sample collection	Biomarker sample collection
Ice Bucket Test	ClearHeart©
Neuropsychology Testing (CAARS, CES-D, BAI, ASI [Pre/Post mTBI], BSI-18 [Pre/Post mTBI]).	Neuropsychology Testing (CAARS, CES-D, BAI, ASI [Pre/Post mTBI], BSI-18 [Pre/Post mTBI]).
Neurologic Evaluation	Neurologic Evaluation
ClearNeck©	ClearNeck©
ClearHeart©	Ice Bucket Test
Buffalo Concussion Bike Test	Buffalo Concussion Bike Test
Randomize subject to Exercise or Stretching Group	
Dispense i-touch or i-phone with appropriate software loaded (whether randomized to graded exercise vs. passive stretching). Subject to enter test PCSS and Godin score via ClearPlay App©; to ensure subject is able to use this App.	Dispense i-touch or i-phone with appropriate software loaded (whether randomized to graded exercise vs. passive stretching). Subject to enter test PCSS and Godin score via ClearPlay App©; to ensure subject is able to use this App.
Adverse Events	Adverse Events

Post-study survey to be completed at Day 56 only

Abbreviations: ASI = Anxiety Sensitivity Index, BAI = Beck Anxiety Inventory, BESS = Balance Error Scoring System, BSI = Brief Symptom Inventory, CAARS = Conners' Adult Attention Deficit Hyperactivity Disorder Rating Scale, CES-D = Center for Epidemiologic Studies - Depression Scale, DNA = deoxyribonucleic acid, PCSS = Post-Concussion Symptom Scale, RNA = ribonucleic acid, VOMS = Vestibular-Oculomotor Screening

Table 5: Schedule of Events

Study Assessments	Baseline Visit		Therapy Period	Telephone Safety Visit	Follow-Up/ET
	Day 0 (within 3 to 14 days of concussion)		Day 1 to Day 55	Day 14, Day 28, Day 42 (± 2 days)	Day 56 (± 3 days)
	Screening Evaluation	Study Evaluation			
Study Assessments					
Informed consent	X				
Allocate unique subject study identification	X				
Inclusion/exclusion criteria review	X				
Demographic data	X				
Medical and medication history	X				
Review of CT or MRI (if obtained)	X				
Height and weight ^a	X				X
Subject Completed Questionnaires					
Post-Concussion Symptom Scale (pre- and post-mTBI)		X	X		
Godin leisure time exercise questionnaire ^b		X	X		X

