9.3.3 Efficacy Population

The efficacy population will include all randomized subjects who completed, at least Day 1 of therapeutic intervention, who had PCSS data at baseline and at least 1 post-baseline assessment and will be based on the actual therapy received. The efficacy population will be

used for the summaries of all neuropsychology and autonomic data, and for the validation of ClearHeart© and ClearNeck© performance.

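### Section 9.3.3 confines the ClearHeart and ClearNeck validation to the efficacy population, so valid Day 0 pairs taken before randomisation can be dropped for reasons unrelated to the devices

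*Protocol*

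**What the plan says.** Protocol 9.3.3 defines the efficacy population as "randomized subjects who completed, at least Day 1 of therapeutic intervention, who had PCSS data at baseline and at least 1 post-baseline assessment". It groups these subjects by the therapy they actually had, and uses the set for the neuropsychology and autonomic summaries and "for the validation of ClearHeart© and ClearNeck© performance". No other section gives the device validation a different set.

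On timing, Protocol 4.1 places randomisation after the autonomic tests: "when the subject has completed all of their Baseline physiologic testing (Ice Bucket Test, ClearHeart© and BCBT) on Day 0". Section 6.3.2 repeats this: "Randomization of each subject will occur when the subject has completed all of their Baseline physiologic testing on Day 0". In Table 4 (Section 8.1) the entry "Randomize subject to Exercise or Stretching Group" stands below the ice bucket test, ClearHeart, the neurologic evaluation, ClearNeck and the bicycle test, for both odd and even subject numbers. Section 7.6 adds the order within the neck pair: "The neurologic examination will be completed first followed by the ClearNeck© assessment".

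On analysis, Table 1 (Section 4.2) specifies for heart rate that "Bland-Altman plots will be used to evaluate the agreement between HR measured by ClearHeart© and ice bucket testing". It plans the same for blood pressure, and a correlation of ClearNeck results with the neck findings on neurologic examination.

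**The concern.** A method-comparison study needs one thing from each subject: a valid reading by both methods at the same visit. At Day 0 that pair exists before any condition that depends on randomisation, therapy or follow-up can be met. Later events that say nothing about either device then decide whether the pair is used. The conditions suit a summary of response to therapy; for device agreement they have no purpose.

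Two things are at stake. The first is precision, because usable pairs are set aside. The second is who the results describe: a set filtered on having started therapy may differ from everyone who can be tested with the device. The treatment comparison is not involved.

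**Working it through.** **Plan's own figure.** The protocol states no sample size or precision for the device validation, so there is nothing on this point to reproduce. Its only computed sample size, 316 for symptom resolution (Section 9.1), has no bearing here. For completeness, a two-sided, continuity-corrected two-proportion calculation with 80% versus 93%, 90% power and α = 0.05 gives 159 per arm, or 318.

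**Step 1: conditions against what the analysis uses.**

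| Condition in 9.3.3 | Known at the time of the Day 0 pair? | Used by the agreement or correlation analysis? |
|---|---|---|
| Randomised | No, it follows the tests | No |
| At least Day 1 of therapy completed | No | No |
| Baseline PCSS | Collected at baseline | No |
| At least one post-baseline assessment | No | No |

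The parenthesis in 4.1 names the ice bucket test, ClearHeart and the bicycle test, but not ClearNeck. That the ClearNeck pair precedes randomisation therefore rests on Table 4, and on 6.3.2, which requires all baseline assessments to be completed.

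**Step 2: size of the loss.** Inputs: 400 subjects to be randomised (9.1), and a 15% attrition allowance (9.1), used only as a ceiling. The fraction failing the 9.3.3 conditions is not given, so 2% to 15% is assumed.

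Approximate 95% half-widths, the first two in units of the SD of the paired difference:

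- mean difference: 1.96/√N
- a limit of agreement: 1.96 × √(1/N + 1.96²/(2(N − 1)))
- ClearNeck correlation on the Fisher z scale: 1.96/√(N − 3)

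For N = 400 the limit of agreement gives 1.96 × √(0.0025 + 3.8416/798) = 1.96 × 0.0855 = 0.168.

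| Assumed loss | Pairs dropped | N | Mean difference | Limit of agreement | Fisher z | Limit-of-agreement half-width relative to N = 400 |
|---|---|---|---|---|---|---|
| 0% | 0 | 400 | 0.098 | 0.168 | 0.098 | 1.00 |
| 2% | 8 | 392 | 0.099 | 0.169 | 0.099 | 1.01 |
| 5% | 20 | 380 | 0.101 | 0.172 | 0.101 | 1.03 |
| 10% | 40 | 360 | 0.103 | 0.177 | 0.104 | 1.05 |
| 15% | 60 | 340 | 0.106 | 0.182 | 0.107 | 1.085 |

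The last column agrees with the simple ratio √(400/N): √(400/392) = 1.01 and √(400/340) = 1.085. Subjects tested but never randomised would come on top of the 400; the documents give no number for them.

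**Step 3: how far selection could move the result.** Suppose, purely as an assumption, that the mean paired difference in the dropped subjects lies one full SD from that in the retained subjects. Dropping a fraction f then moves the estimated mean difference by f × 1 SD: 0.02 SD at 2%, 0.05 SD at 5%. Both are smaller than the half-width of 0.098 SD at N = 400. At the 15% ceiling the shift would be 0.15 SD, which is larger, but that needs both the ceiling loss and the full-SD contrast.

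**The case against.** The other side has several good points.

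- **The bar is low.** One day of therapy and one later assessment suffice, and the PCSS is reported daily (7.4.1). Withdrawal for non-upload needs seven consecutive days (5.3.1, 6.4.4), and withdrawal for over-exercise arises during therapy. Most withdrawn subjects would already have met the Day 1 condition and would stay in the set. This stands: 15% is a ceiling and not an expected loss.
- **Few subjects should be tested but not randomised.** Section 6.3.2 settles eligibility before the baseline assessments, and randomisation follows on the same day. Symptom worsening ends the bicycle test (7.5.2) but is not stated as a bar to randomisation. This stands.
- **Selection is conjecture.** A reader might infer that the lost subjects are those with the most autonomic impairment, since the bicycle test provokes symptoms just before randomisation. No section says that such subjects fail to start therapy, or that device differences depend on impairment. Agreement shifts only if exclusion is related to the paired difference itself.
- **9.3.3 is easily over-read.** A reader might take actual therapy received as a further entry condition, but it is a grouping rule and excludes nobody. A reader might also take the post-baseline assessment to be a PCSS; that is the natural reading, but the wording does not fix it. Completion of Day 1 is required either way.
- **One set for both visits is a defensible convention.** The device tests are repeated at Day 56 (Table 5), where the rule should remove almost nobody. That leaves the Day 0 pairs unanswered.

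The list of tables titles Table 4 as following randomisation. The table body, 4.1 and 6.3.2 all put randomisation after the tests, so this does not rescue the rule. Nor can the matter be left to the SAP: the protocol fixes the set itself, and 9.2 has the SAP carry out the protocol's principal features.

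**Conclusion.** The point holds in limited form. As written, 9.3.3 excludes valid Day 0 device pairs on conditions that neither the devices nor the planned validation analyses involve. The cost in precision is small: about 1% wider limit-of-agreement intervals at an assumed 2% loss, and about 8.5% at the 15% ceiling, both from a base of 400 pairs. The true loss is not stated and is probably near the lower end.

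The documents do not support the stronger claim that the validation would be biased towards less impaired subjects; that remains a possibility only. Stakes are low: Section 3.2 makes ClearHeart validation a secondary objective and 3.3 makes ClearNeck exploratory (Table 1 lists both among the secondary ones), and the comparison of the arms is unaffected. It merits a short clarification and nothing more.

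**What to change.** In Section 9.3, add a device-validation set: all consented subjects with a valid ClearHeart and ice bucket pair, or a valid ClearNeck and neck examination pair, at the visit analysed, regardless of randomisation, therapy or PCSS status. Remove device validation from the uses listed in 9.3.3.

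The cost is a few sentences and no new tests, but it is not quite free. Section 11.2 requires complete data collection only for subjects who sign consent and also start therapy. Unless that is aligned, Day 0 device data from non-starters may not reach the eCRF, and these are the subjects whom the new set would add. Section 11.2 should therefore state that Day 0 device and reference results are entered for every consented subject who was tested. This is best settled early, before such records are left incomplete.

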9.4 Demographic and Other Baseline Characteristics

Subject enrolment and disposition will be summarized by randomized treatment group and will include the total number of subjects randomized into the study and in each analysis population. The number of subjects prematurely discontinuing from the study, along with the reason for early discontinuation will also be summarized.

Demographic and baseline data recorded at screening and prior to dosing will be summarized, by randomized treatment group.

9.5 Safety Analysis

9.5.1 Adverse Event Analysis

Adverse events will be coded using the Medical Dictionary for Regulatory Activities (MedDRA). AEs will be grouped by system organ class and preferred term and summarized, by treatment group at the time of onset of the AE (ie, the therapeutic intervention most recently prior to the onset of the AE). The summary tables will present the number and percentage of total subjects and number of events, by system organ class and by preferred term.

All AE summaries will be restricted to treatment emergent AEs only. Treatment emergent AEs are defined as AEs which commence on or after the time of start of therapeutic intervention.

For the summaries of AEs, subjects who experience the same AE (in terms of the MedDRA preferred term) more than once will only be counted once for that event in the number of subjects but all occurrences of the same event will be counted in the number of events.

Separate summaries will be provided for AEs by severity and relationship to study intervention.

Serious adverse events will be summarized and listed separately.

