4.2 Study Objectives and Endpoints

The study objectives and endpoints to be evaluated in this study are presented in Table 1.

Table 1: Study Objectives and Endpoints

Objectives	Endpoints
Primary Objectives	Primary Endpoints
To compare the effects of graded exercise to passive stretching using ClearPlay© on symptomatic recovery rate following mTBI.	
 • Within-subject analysis of change in symptoms over time using the PCSS, comparing short-term ‘survival rates’ between graded exercise and stretching using Kaplan-Meier analyses for days since concussion.
Secondary Objectives	Secondary Endpoints
To compare the safety and tolerability of graded exercise to passive stretching in patients following mTBI.	
 • Adverse events reported from Day 1 through Day 56, including those identified during exercise or passive stretching during the 20 minutes of daily therapy.
To compare symptom resolution following graded exercise compared to passive stretching using ClearPlay© following mTBI.	
 • Within subject analysis of change in the number of subjects who are symptom free at 8 weeks between the 2 groups. Symptom free is defined by subjects having 3 consecutive days of PCSS scores lower than pre-concussion. 
Note: This objective is similar to the primary one, with the primary endpoint being recovery (binary outcome) vs. symptom resolution (continuous variable).
 
 • Determine differences in symptomatic recovery based on gender, baseline scores on the PCSS, baseline athletic fitness (Godin leisure-time exercise questionnaire), the history of injury, a history of migraine, as well as the presence of pre-morbid anxiety.
To compare the effects of graded exercise to passive stretching using ClearPlay© on physiologic recovery rate following mTBI.	
 • Within subject analysis of normalization of physiologic measurements obtained during the BCBT comparing data collected on entry to the study on Day 0 vs. follow up on Day 56 including: 
 - Beat to beat BP; • Determine differences in physiologic recovery based on gender, baseline scores on the PCSS, baseline athletic fitness (Godin leisure-time exercise questionnaire), the history of injury, a history of migraine, as well as the presence of pre-morbid anxiety (BAI; BSI-18; ASI).

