7.1.5.11 Recording of Adverse Events

Adverse events will be recorded and reported from Day 1 to Day 56. Adverse events will be captured at clinic visits on Day 1 and Day 56, and at telephone safety visits on Day 14, Day 28 and Day 42.

When an AE/SAE occurs, it is the responsibility of the investigator to review all documentation (eg, hospital progress notes, laboratory, and diagnostic reports) relative to the event. The investigator will then record all relevant information regarding an AE/SAE in to the eCRF. All details of any treatments initiated due to the AE should also be recorded in the subjects' notes and the eCRF.

Each AE will be documented in the subject's eCRF. If an AE changes in frequency or intensity during a study, a new entry of the event must be made in the eCRF.

In the event where the principal investigator is not a clinician, then the principal investigator must delegate the safety review duty to a clinician.

The investigator will attempt to establish a diagnosis of the event based on signs, symptoms, and/or other clinical information. In the absence of a diagnosis, the individual signs/symptoms should be documented.

All AEs occurring during the study must be documented on the relevant eCRF pages. The following data should be documented for each AE:

- Description of the symptom event;
- Classification of ‘serious’ or ‘not serious’;
- Severity;
- Date of first occurrence and date of resolution (if applicable);
- Action taken;
- Causal relationship;
- Outcome of event (unknown, recovered, not yet recovered, recovered with sequelae, death [with date and cause reported]).

After the initial AE or SAE report, the investigator is required to proactively follow each subject and provide further information to the sponsor on the subjects’ condition.

All AEs are required to be assessed by a medical practitioner. All AEs or SAEs documented at a previous visit/contact that are designated as ongoing, will be reviewed at subsequent visits/contacts. All AEs or SAEs will be followed until resolution, until the condition stabilizes, until the event is otherwise explained, or until the subject is lost to follow-up. The investigator will ensure that follow-up includes any supplemental investigations as may be indicated to elucidate the nature and/or causality of the AE or SAE.

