Brief Symptom Inventory (pre- and post-mTBI)		X			X ^f
Anxiety Symptom Index (pre- and post-mTBI)		X			X ^f
Beck Anxiety Inventory		X			X
CAARS (Attention)		X			
CES-D (Depression)		X			

CONFIDENTIAL

Study Assessments	Baseline Visit		Therapy Period	Telephone Safety Visit	Follow-Up/ET
	Day 0 (within 3 to 14 days of concussion)				
	Screening Evaluation	Study Evaluation	Day 1 to Day 55	Day 14, Day 28, Day 42 (±2 days)	Day 56 (±3 days)
Post-study survey					X
Autonomic Tests					
Ice Bucket Testing		X			X
ClearHeart© Testing		X			X
Buffalo Concussion Bike Test		X			X
Other Physical Tests					
ClearNeck© Testing		X			X
Neurologic Testing		X			X
Biomarkers/BioBank					
Biomarker sample collection		X			X
DNA and RNA sample collection		X			X ^d
Therapeutic Intervention					
Dispense i-touch or i-phone.		X			
Waveband® – dispense and instruct		X			
ClearPlay© - dispense and instruct via initial entry of PCSS and Godin data on i-touch or i-phone		X			
Enter/Review ClearPlay© mobile application entries			X ^e		
Return of Waveband®					X

CONFIDENTIAL

Study Assessments	Baseline Visit		Therapy Period	Telephone Safety Visit	Follow-Up/ET
	Day 0 (within 3 to 14 days of concussion)		Day 1 to Day 55	Day 14, Day 28, Day 42 (±2 days)	Day 56 (±3 days)
	Screening Evaluation	Study Evaluation			
Safety Assessments					
Vital signs including beat to beat BP		X			X
Adverse event monitoring		X	X	X	X
Concomitant medications		X	X	X	X
Concomitant therapies		X	X	X	X

Abbreviations: AE = Adverse Event, ASI = Anxiety Sensitivity Index, BAI = Beck Anxiety Inventory, BESS = Balance Error Scoring System, BP = blood pressure; BSI = Brief Symptom Inventory, CAARS = Conners' Adult Attention Deficit Hyperactivity Disorder Rating Scale, CES-D = Center for Epidemiologic Studies - Depression Scale, CT = DNA = deoxyribonucleic acid, , ET = early termination, MRI = magnetic resonance imaging, mTBI = mild traumatic brain injury, PCSS = Post-Concussion Symptom Scale, RNA = ribonucleic acid, VOMS = Vestibular-Oculomotor Screening

Footnotes for Table 5

- Height will only be captured at the Screening Visit;
- Godin leisure time exercise questionnaire to be administered weekly;
- Optional consent required;
- RNA collection only;

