9.3.2 Safety Population

The safety population will include all randomized subjects who completed at least Day 1 of therapeutic intervention and will be based on the actual therapy received, if this differs from that to which the subject was randomized to. The safety population will be used for the summaries of all safety data.

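### The start of AE recording is contradictory (Day 1 in the text, Day 0 in Tables 4 and 5), and Section 9.5.1 leaves non-serious AEs from the Day 0 tests out of every AE summary

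*Protocol*

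**What the plan says.** **Recording window.** Section 7.1.5.11 says "Adverse events will be recorded and reported from Day 1 to Day 56" and continues: "Adverse events will be captured at clinic visits on Day 1 and Day 56". The safety endpoint in Table 1 (Section 4.2), repeated in the synopsis, has the same window: "Adverse events reported from Day 1 through Day 56, including those identified during exercise or passive stretching during the 20 minutes of daily therapy".

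**Visits.** Section 4.1 has two clinic visits. The first is "Study Visit 1 (Day 0) – Screening/Baseline visit: within 3 to 14 days of concussion"; the second is Day 56. The contacts between them are by telephone.

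**Schedule.** In Table 5 (Section 8.1) the row "Adverse event monitoring" is marked at the Day 0 study evaluation, in the therapy period, at the telephone visits and at Day 56. Table 4 ends its order of assessments with adverse events.

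**Analysis.** Section 9.5.1 says "All AE summaries will be restricted to treatment emergent AEs only" and then "Treatment emergent AEs are defined as AEs which commence on or after the time of start of therapeutic intervention". Relationship summaries are planned for the study intervention; none is planned for the device. Section 9.3.2 defines the safety population as "all randomized subjects who completed at least Day 1 of therapeutic intervention".

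**The concern.** ClearHeart is a prototype under validation. The protocol defines adverse device effects (7.1.5.2), requires a device-causality assessment for every AE (7.1.5.10), names hand discomfort from cooling as a risk in some subjects (2.4), and counts exercise testing among the risks to be monitored (2.6). The bicycle test may run to exhaustion (7.5.2). Each subject's first exposure to these procedures, and the one closest to the injury, is on Day 0.

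Two things are at stake. Sites are given conflicting instructions on whether an AE on Day 0 has to be recorded. And a Day 0 AE that is recorded has no place in the planned summaries, so the report would describe tolerability of the tests from the Day 56 repeats alone, in subjects who started therapy and came back.

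**Working it through.** No figure in the protocol needs to be reproduced here. The check sets the timeline against the rules, then counts sessions.

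**1. When the tests happen.** Sections 4.1 and 6.3.2 place randomization after completion of the Day 0 physiologic tests. Table 4 puts blood or saliva sampling, ice bucket, ClearHeart, ClearNeck and the bicycle test ahead of the randomization step. The synopsis starts therapy on Day 1. All first sessions therefore precede therapy.

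**2. Is a Day 0 AE recorded?**
- Section 7.1.5.11 and the endpoint in the synopsis and Table 1: no, the window opens on Day 1.
- Tables 4 and 5: yes, AE capture is scheduled at the Day 0 visit.
- Section 7.1.4: a clinically significant abnormal vital sign is to be reported with an AE, and Table 5 schedules vital signs on Day 0. The protocol can thus call for an AE report that falls outside its own stated window.
- The Day 1 clinic visit in 7.1.5.11 matches no visit in Section 4.1.

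This is a contradiction, and the text does not settle it.

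**3. Is a recorded Day 0 AE summarized?** Onset on Day 0 is before therapy start, so the event is not treatment emergent and Section 9.5.1 excludes it. That section also tabulates by the intervention most recently preceding onset; a Day 0 event has none, hence no column. The answer is the same whichever recording start applies.

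**4. Is the subject in the denominator?** Only if randomized and through Day 1 of therapy (9.3.2). Section 11.2 likewise requires completed data collection for those who sign consent and commence therapy. A subject who has an AE on Day 0 and never starts meets neither condition.

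**5. Share of sessions on Day 0.** Inputs: 400 subjects and 15% attrition (Section 9.1); one session of each test on Day 0 and one on Day 56 (Table 5).
- Full Day 56 attendance: 400 / (400 + 400) = 400 / 800 = 50%.
- All of the attrition misses Day 56 (assumption): 400 × 0.85 = 340; 400 / (400 + 340) = 400 / 740 = 54%.

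For the ice bucket, ClearHeart and bicycle tests together this is 1,200 of 2,400, or 1,200 of 2,220, with the same percentages. These are sessions. The protocol gives no AE rate for any test, so they cannot be turned into a number of events.

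**The case against.** A reader might infer that AEs are simply not recorded before Day 1 and that harms from the Day 0 tests vanish from the safety results. The documents do not support that.

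- Tables 4 and 5 schedule capture on Day 0, and Sections 7.1.5.1 and 7.1.5.11 ask for all AEs during the study to be documented. Section 9.6 also places the baseline ice bucket test on Day 1, so Day 1 in these places may be a slip for the baseline visit.
- The restriction in 9.5.1 is on summaries. Listings are not expressly limited, and SAEs are also listed separately.
- SAEs, SADEs and device deficiencies with SADE potential go to the sponsor within 24 hours with no therapy-start limit (7.1.5.13). Device deficiencies are documented throughout (7.1.5.12).
- AEs from the Day 56 tests are kept. A Day 0 AE that later changes in frequency or intensity gets a new entry (7.1.5.11) and might then count as treatment emergent.
- Minute-by-minute symptom ratings are taken in the bicycle test (7.5.2), and its results are summarized by time point (9.6.2).

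Those limits stand. It is also fair to say that the safety objective compares the two therapies, that Day 0 events cannot inform that contrast, and that the protocol sets no separate safety objective for ClearHeart. The treatment-emergent tables are therefore right for the arm comparison.

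What the objection does not remove is the remainder. Reading Day 1 as a slip settles recording only, and 9.5.1 still excludes the event. Nor can this be left to the SAP as detail: Section 9.2 has the SAP follow the protocol's principal features, and 9.5.1 sets an explicit rule for all AE summaries. An extra listing would not conflict with that rule, but the protocol does not plan one.

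**Conclusion.** The point holds within limits. The start of AE recording is internally contradictory and needs to be reconciled. Independently of that, non-serious AEs that begin in the Day 0 procedures enter no planned AE summary unless they worsen after therapy starts and are re-entered, and subjects who never start therapy are outside the safety population.

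Between 50% and 54% of the scheduled sessions of each test lie on Day 0. The upper figure assumes that every dropout misses Day 56; Sections 5.3.1 and 5.3.2 seek follow-up assessments at early termination, so the true share may be nearer 50%. The percentage measures exposure. It does not say that half of the harms are lost, and that number cannot be derived from the protocol. The comparison of exercise with stretching is not biased by this.

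**What to change.** 1. Reconcile Section 7.1.5.11, the synopsis and Table 1 with Tables 4 and 5, so that AEs are recorded from the first Day 0 study procedure, and correct the Day 1 clinic visit to Day 0.
2. In Section 9.5.1, keep the treatment-emergent tables for the arm comparison.
3. Add to Section 9.5.1 one pooled summary or listing of procedure- and device-related AEs on Day 0 and Day 56. Its denominator should be everyone who underwent a test, whether or not they were randomized or started therapy.

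The cost is a few edited sentences and one extra table. AE monitoring on Day 0 is already in Table 5 and device causality is already assessed for each AE. The one practical addition is that AE data must also be completed for tested subjects who never start therapy, so the data-collection sentence in Section 11.2 should be aligned.
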